5.2.6.7 Concomitant medication

Two tables with the proportions of subjects in the SAF population taking each concomitant medication will be provided for:

- Concomitant medications at baseline (started before baseline and stopped after baseline or still ongoing at end of treatment) by treatment group (Statistical table 14.3.13.1).
- Concomitant medications started after baseline by treatment group (Statistical table 14.3.13.2).

Tables summarizing the use of pirfenidone and nintedanib (proportion of patients using each drug) at baseline and started after baseline by treatment group will be prepared on the SAF population (Statistical table 14.3.13.3, 14.3.13.4).

5.3 Statistical/Analytical issues

5.3.1 Adjustments for Covariates

All comparisons of change from baseline to a given visit between treatment groups performed using ANOVA models and pooling subjects on a stable dose of pirfenidone or nintedanib with subjects not on other treatment for IPF, are adjusted for stratification levels.

Analysis of time variation in a given variable using Linear Mixed Models and pooling subjects on a stable dose of pirfenidone or nintedanib with subjects not on other treatment for IPF, are all adjusted for baseline measurements of the response variable and stratification levels.

5.3.2 Handling of Dropouts or Missing Data

Missing data in efficacy analysis:

The statistical model (linear mixed models for repeated measures) used for the primary and most secondary efficacy analyses will be used without imputation of missing values and are valid under the assumption of missingness at random.

Multiple imputation techniques will be used for the sensitivity analysis on the initially planned primary analysis (see Section 5.2.5.1).

All available efficacy and safety data will be included in data listings and tabulations.

Missing or incomplete dates:

For all listings, missing or incomplete dates will be left as they were recorded.

For calculation / sorting / assignment based on dates (*e.g.*, treatment emergent AEs, concomitant medications...), the following rules will apply:

- The most conservative approach will be considered (*i.e.*, if the onset date of an AE/concomitant medication is missing / incomplete, it will be assumed to have occurred during the study treatment phase (*i.e.*, a TEAE for AEs) except when the partial onset date or other available data indicates differently (*e.g.*, start date day missing, but month before the month of baseline date, or stop date before baseline date).
- Medical history or disease diagnosis with missing/incomplete date will be assumed to have occurred before any study treatment except when the partial onset date or other available data indicates differently.
- Assignations based on dates will be reviewed and confirmed or infirmed during the data review meeting
- Missing or partial start or end dates of IMP administration, if any, will be reviewed during the data review meeting.

5.3.3 Interim Analyses and Data Monitoring

No formal interim data analysis is planned for the study.

A blinded DMC will be established to review safety data from this study, thereby better ensuring the safety of study participants. Consistent with US Food and Drug Administration (FDA) recommendations (FDA Guidance for Industry, Establishment and Operation of Clinical Trial Data Monitoring Committees, 2006), the DMC will be constituted of independent clinicians expert in the field of IPF and clinical research. A formal charter will be established for the conduct of the DMC.

The committee is planned to review the safety data in an unblinded manner, and the efficacy data will be provided semi-blinded by group. However, DMC may request study drug treatment code for group in order to complete their assessment of safety/benefit risk. This request will only be made to the unblinded statistician, as stated in the DMC Charter.

5.3.4 Multicentre studies

This study is planned to be conducted in 18 study sites in 8 countries. Because of the too small expected numbers of patients within sites, all the analysis will be performed on the pooled data over countries and study sites.

5.3.5 Multiple Comparison/Multiplicity

There will be one single primary efficacy analysis, from which the conclusions on efficacy will be drawn. Consequently, there is no issue of multiplicity of primary analyses and no need to adjust the significance level.

5.3.6 Use of an "Efficacy Subset" of Patients

Two efficacy analyses populations are defined, the ATS and the PP. The definition of these populations is available in Section 3. The primary efficacy analysis will be conducted on the ATS. No patient with available post-treatment efficacy data are excluded from the ATS and, consequently from the primary efficacy analysis.

The PP population will be used to conduct a sensitivity analysis and assess the robustness of the primary efficacy analysis conclusions. Any substantial difference between the two analyses will be explored and discussed.

In addition, the SAP planned to conduct the primary analysis on the Full analysis Set. This was then changed to the ATS. Nevertheless, the initially planned analysis on the FAS will be conducted and provided as an additional sensitivity analysis to further assess the robustness of the primary efficacy analysis conclusions and in particular to assess the impact of excluding patient without any post-baseline efficacy measurement from the FASATS population. Any substantial difference with the result obtained for the primary efficacy analysis on the ATS will be explored and discussed.

5.3.7 Active-Control Studies Intended to Show Equivalence

Not applicable.

5.3.8 Examination of Subgroups

Sensitivity analysis of the primary endpoint and some secondary efficacy analyses aim at exploring difference in response variables between the levels of stratification. See sections 5.2.5.1 and 5.2.5.2 for details.

5.4 Data handling conventions

5.4.1 Baseline definitions

For both the efficacy and safety endpoints the last observation prior to the first dose of study treatment administration will be used as the baseline value. This will usually correspond to the measurement performed at day1 week 0 before first-dose. However, in case of missing value at day 1 week 0 the last available value recorded during screening will be used as baseline value.

5.4.2 Retest, Outliers

5.4.2.1 Retests

The retests will be managed as follow:

- Any retest before baseline : the last available value recorded before baseline (day1 week 0) will be used as the baseline
- Any other retest: data will be reviewed and decision will be made during the blind review on the basis of the following rules:
 - Retest on efficacy data: non-missing value the closest to the scheduled visit will be used
 - Retest on safety data: the worst recorded value will be used

5.4.2.2 Outliers

All outlier data will be reviewed during the data review meeting and decisions regarding their use in the statistical analyses will be made.

5.4.3 Unscheduled visits

All unscheduled visit data will be presented in the individual data listings and used in all safety analyses. For categorical results: reallocation to the visit following last infusion. In case of several data the worst observation will be used in tabulation. For numeric results the first value among worst abnormality/grade will be used. These reallocation will be reviewed in blind review meeting.

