3.2. Secondary Endpoints

The secondary endpoints for the study are:

1. Structural Imaging:

- Mean change from Baseline to Week 28 in total lung volume and volume of parenchymal features on HRCT (in ml and % of total lung volume) representative of interstitial lung abnormalities (ILA), including ground glass density, reticular changes, and honeycombing, using quantitative imaging software.
- Mean change from Baseline to Week 28 in volume of parenchymal features on HRCT (in ml and % of total lung volume) representative of normal lung (non-ILA), including normal and mild low attenuation areas, using quantitative imaging software.
- Correlation between mean change from Baseline to Week 28 in FVC % predicted and mean change from Baseline to Week 28 in total lung volume and volume of parenchymal features on HRCT (in ml and % of total lung volume) representative of interstitial lung abnormalities (ILA), including ground glass density, reticular changes, and honeycombing by quantitative imaging software.

2. Safety: Tolerability/safety will be assessed over the 28-week study period by the following parameters:

- Incidence of AEs.
- Incidence of serious adverse events (SAEs).
- Incidence of respiratory AEs and SAEs.
- Proportion of subjects discontinuing study drug due to AEs.
- Change from Baseline in hematology and serum chemistries.
- All-cause mortality.
- Mortality due to respiratory deterioration.

3. Disease related events associated with mortality: The number of “respiratory decline” events over the 28-week study period as defined below:

- Unscheduled visits to a healthcare professional for respiratory status deterioration.
- Urgent care visits for respiratory status deterioration.
- Hospitalization due to a worsening or exacerbation of respiratory symptoms.

All “respiratory decline” events will be further characterized according to the definitions of IPF-related acute exacerbation, as proposed by an expert committee sponsored by the IPF Clinical Research Network and the National Heart Lung and

Blood Institute (NHLBI) (Collard, Moore et al. 2007) and applied by (Collard, Yow et al. 2013)

- Acute onset of symptoms (< 30 days in duration)
- New radiographic abnormalities (bilateral ground glass or consolidation on HRCT with no pneumothorax or pleural effusion)
- The absence of an identified infectious etiology by routine clinical practice
- Exclusion of alternative causes by routine clinical practice, including:
 - a. Left heart failure

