5.2.6.4 Laboratory safety variables

Table of laboratory safety variables:

Laboratory evaluations will be summarized by visit and by treatment group on the SAF population. For each hematology, chemistry and coagulation variables we will compute:

- Quantitative descriptive statistics on both raw values and change from baseline (Statistical tables 14.3.8.1-2, 14.3.9.1-2 and 14.3.10.1-2)
- Qualitative descriptive statistics (individual patient changes):
 - Number of patients with values: normal, abnormal NCS, abnormal CS (Statistical table 14.3.8.2, 14.3.9.2 and 14.3.10.3)
 - Shift Tables from baseline to each visit (Statistical table 14.3.8.3, 14.3.9.3 and 14.3.10.3)

Depending of their number the clinically significant laboratory abnormalities will not be tabulated but rather presented in individual data listings (Listings 16.2.8.1 to 16.2.8.4).

Figures on laboratory safety variables:

All individual values of a given laboratory measurement for each patient will be produced. When available, the LLN and ULN will be displayed on the graph. Figures will be produced for all hematologic, chemistry and coagulation variables (Figures 14.3.2).

To facilitate the exploration of potential Drug-Induced Liver Injury (DILI), eDISH (Evaluation of Drug-Induced Serious Hepatotoxicity) plots, plotting peak total bilirubin level versus peak ALT level, both expressed as multiples of the upper limit of normal on a base 10 logarithmic scale, together with mlines identifying the normal range and 2 times the upper lipit of the normal range for total bilirubin and three times the upper limit of the normal range for ALT, will be presented (Figure 14.3.3).

Listing of laboratory safety variables:

Listings of all safety-related laboratory test including pregnancy test (Listings 16.2.8.1 to 16.2.8.4) will be prepared, presenting patient id, identification of time point, age, sex, race-ethnicity, weight, identification of laboratory test, raw result, evaluation (normal, abnormal...), investigator judgment on clinical significance on abnormal values. This listing will be presented by treatment group.

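### Worst-value selection of repeat and unscheduled safety results (SAP 5.4.2.1, 5.4.3) is not kept out of the mean and change-from-baseline tables, whose baseline is a single unselected value

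*SAP*

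**What the plan says.** **After baseline, repeats.** SAP 5.4.2.1 states: "Retest on safety data: the worst recorded value will be used". The choice is made before unblinding, but not freely: "data will be reviewed and decision will be made during the blind review on the basis of the following rules". For efficacy retests the same section uses a neutral rule, the available result nearest the planned visit.

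**After baseline, unscheduled results.** SAP 5.4.3 states: "All unscheduled visit data will be presented in the individual data listings and used in all safety analyses". Two selection rules follow. For categorical results, which are moved to the visit after the last infusion, "In case of several data the worst observation will be used in tabulation". For numeric results, "For numeric results the first value among worst abnormality/grade will be used". The reallocation sentence names categorical results only, so the visit to which a numeric unscheduled value belongs is not stated.

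**Before the first dose.** SAP 5.4.1: "the last observation prior to the first dose of study treatment administration will be used as the baseline value". SAP 5.4.2.1 confirms that a retest before baseline is resolved by taking the last value, not the worst.

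**Where the values go.** SAP 5.2.6.4 plans, by visit and arm, "Quantitative descriptive statistics on both raw values and change from baseline" for haematology, chemistry and coagulation. SAP 5.2.6.6 plans the same kind of summary for vital signs, including means. Protocol 3.2 lists among its secondary safety parameters "Change from Baseline in hematology and serum chemistries". No section restricts these summaries to scheduled values.

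**The concern.** Choosing the worst of several results is a sound, conservative rule for counting abnormalities. It does not suit a mean change. If the later value is picked because it is bad and the earlier one is not picked at all, their difference moves even when nothing has happened to the patient. The movement grows with the number of results available, so the summary partly reflects how often a patient was tested.

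At stake is the readability of a listed safety endpoint. If one arm were retested more often, part of any difference in its laboratory or vital-sign means would come from the data-handling rule and not from the drug.

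**Working it through.** The documents give no figure for the effect of these rules, so there is none to reproduce. The effect can be worked out under stated assumptions.

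**Inputs from the documents:** the selection rules and baseline rule above; planned arm sizes of 78 and 39 (SAP 2.3.2); three laboratory classes (SAP 4.2.4); vital-sign limits that are two-sided except for oxygen saturation, which has only a lower limit of 90 (SAP section 8).

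**Assumptions, not in the documents:** no true change; normal errors with independent repeats; 2 to 4 values in a visit interval; 5% to 40% of patients with repeats; intraclass correlation 0.5 to 0.7; one abnormal class, with its limit at 1.96 SD of the population distribution. Shifts are in within-patient SD units, from 1,000,000 simulated patients per case.

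**Step 1. Retest rule, harm in one direction.** The selected value is the maximum of k values, and baseline has expectation zero.
- k = 2: 1/√π = 0.56 (simulated 0.564)
- k = 3: 3/(2√π) = 0.85 (simulated 0.846)
- k = 4: 1.03 (simulated)

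**Step 2. Unscheduled rule, harm in one direction.** This rule takes the earliest value in the worst class. If all values are normal, that is simply the first value, so selection acts only when a limit is crossed.
- Limit at 1.96 SD: 0.03 to 0.04 for k = 2, and 0.06 to 0.08 for k = 3
- Limit close on one side (+0.8 and −3 SD, intraclass correlation 0.6): 0.18 for k = 2, 0.30 for k = 3

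**Step 3. Symmetric two-sided limits.** The mean shift is about 0.00 under either rule. The SD of change, √2 = 1.41 without selection, rises to 1.44–1.49 for the first value in the worst class. It rises to 1.51–1.65 if worst means the most extreme value in either direction.

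**Step 4. Arm difference under the retest rule.** Arm shift = share of patients with repeats × per-patient shift. The difference is (share A − share B) × shift.

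| Share with repeats (assumed) | k = 2 | k = 3 |
|---|---|---|
| 10% vs 10% | 0 | 0 |
| 20% vs 10% | 0.06 | 0.08 |
| 30% vs 10% | 0.20 × 0.564 = 0.11 | 0.20 × 0.846 = 0.17 |
| 30% vs 5% | 0.14 | 0.21 |
| 40% vs 10% | 0.17 | 0.25 |

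Under the unscheduled rule at 30% vs 10%, the difference is 0.20 × 0.03 = 0.006 to 0.20 × 0.08 = 0.016. With the close one-sided limit it is 0.20 × 0.18 = 0.04 to 0.20 × 0.30 = 0.06.

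**Step 5. Scale.** Standard error of the arm difference in mean change = √2 × √(1/78 + 1/39) = 0.28. Every entry in the table is below it.

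**Step 6. Scheduled value instead.** The expected shift is 0.00 in both arms, whatever the testing frequency.

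**The case against.** The strongest reply is that the effect is small and its direction uncertain. Much of that stands.

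- **The unscheduled rule is mild.** A reader might apply the worst-of-k figures to SAP 5.4.3. Its wording does not support this: it picks a class, then the earliest value in it. The 0.56 and 0.85 figures belong to SAP 5.4.2.1 only.
- **A general bias toward harm does not follow.** Most vital-sign limits are two-sided, and the laboratory plots show both lower and upper limits where available. For symmetric two-sided parameters the spread changes, not the mean.
- **A bias against PRM-151 does not follow.** One might infer that infusion reactions trigger extra tests on active treatment. After a reaction the protocol asks for an ECG and cytokines (6.2, 7.6.2, 7.12.1.2), not haematology or chemistry. The 15-minute infusion readings stay on the source document (7.8). Scheduled testing is the same in both arms, and repeat rates by arm are not given.
- **Repeats may not be independent draws.** If a repeat is taken only because the scheduled value was abnormal, that value is usually the one selected anyway. The shift over the whole arm is then at most about 0.005 SD.
- **A faulty result does not always displace its repeat.** It does so only if it is also the worse one, and SAP 5.4.2.2 sends outliers to review.
- **The tables are descriptive.** No test is planned on them.

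The appeal to blind review does not stand. Reviewers who do not know the arm would still be applying an asymmetric rule. The outlier review states no criterion and does not mention invalid samples.

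**Conclusion.** The point holds in a limited form. The asymmetry comes from stated rules, not from missing detail: post-baseline safety results are selected for being worst, baseline is not, and the selected values are free to enter the mean-change tables. The retest rule carries the larger effect. It moves the mean only for parameters where harm lies in one direction, such as oxygen saturation; elsewhere it mainly widens the spread.

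The sizes rest on assumed numbers of repeats, independence and normal errors. Any between-arm effect rests further on unequal repeat rates, for which the documents offer no evidence; at equal rates it is zero. In the range tried, the largest arm difference is 0.25 SD against a standard error of 0.28 SD. This will not by itself create or hide a safety finding, but it is systematic, affects a listed endpoint and is easy to avoid.

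**What to change.** Amend SAP 5.4.2.1 and 5.4.3 as follows:

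1. Limit worst-value selection to abnormality counts, shift tables, peak-value plots (the eDISH figure) and listings.
2. For means and change from baseline, use the scheduled value or, failing that, the available value nearest the scheduled visit, as is already done for efficacy retests. Use the repeat if the original sample was documented as invalid.
3. State the visit to which a numeric unscheduled value is assigned.

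The cost is two or three sentences and a record-selection flag in the analysis data set, before database lock. No safety signal is lost, because the worst values remain in the outputs named in item 1.

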5.4.4 Visit windowing

The agreement between realized visit date and the expected visit time frame will be reviewed during blind review meeting.

For premature discontinued patient, all data collected during the End of Study visit will be reallocated to the visit following last infusion.

6 Modifications from the statistical sections in the protocol

6.1 Change in the primary efficacy analysis

According to the protocol, the primary efficacy analysis was to be the Full Analysis Set (FAS), defined as all randomized patients having received at least one administration of the study medication with a baseline and at least one post-baseline assessment of FVC [% predicted] (primary efficacy criterion) available.

Limiting the population to subjects having at least one post-baseline assessment of FVC [% predicted] draws the efficacy population further from the intention to treat paradigm than the exclusion of only untreated patients. Consequently, it has been decided to change the primary efficacy analysis population to the All Treated Set (ATS, see section 3.2) defined as all randomized subjects who have received at least one administration of the investigational medicinal product (IMP).

In addition to this change of population, it has been decided to change the analysis model from the initially planned ANOVA model on change from baseline to week 28 to a linear mixed effect model with random intercept using all measurements available until Week 28 used to compute the estimate of the between group difference in change from baseline at week 28.

6.2 Changes in secondary efficacy analyses

All secondary efficacy analyses will be performed on both the ATS and the PP.

To be consistent with the primary efficacy analysis, the same analysis model as those of the primary analysis (see section 5.2.5.1) will be used, instead of the ANOVA model initially planned, to determine the effect size of PRM-151 relative to placebo in change from Baseline to Week 28 in normal lung parenchyma (normal + mild LAA) and interstitial lung abnormalities (ILA) as quantified on high-resolution CT (HRCT) imaging analysis (SO1).

To be consistent with the primary efficacy analysis, the same descriptive statistics and analysis model as those of the primary analysis (see section 5.2.5.1) will be used, instead of the ANOVA model initially planned, to determine the effect size of PRM-151 relative to placebo in change from Baseline to Week 28 in mean FVC% predicted, separately in subjects on a stable dose of pirfenidone or nintedanib and in subjects not on other treatments for IPF (SO2).

To be consistent with the primary efficacy analysis, the same analysis model as those of the primary analysis (see section 5.2.5.1) will be used, instead of the ANOVA model initially planned, to determine the effect size of PRM-151 relative to placebo in change from Baseline to Week 28 in

normal lung (defined as normal + mild LAA) parenchyma and interstitial lung abnormalities (ILA) as quantified on HRCT imaging analysis (SO3).

Odds ratios will be computed in addition to quantitative statistics to determine (SO6) the effect size of PRM-151 relative to placebo on pulmonary function and mean change in FVC% predicted.

To be consistent with the primary efficacy analysis, the same descriptive statistics and analysis model as those of the primary analysis (see section 5.2.5.1) will be used to determine the effect size of PRM-151 relative to placebo on 6MWD (SO7) and DLCO (SO8).

